### 3.2.3 Protocol violations and handling of missing data

Major protocol violations thought to affect the assessment of efficacy of the study drug will be considered. The following situations will be considered as major protocol violations:

- Patients who withdrew or were withdrawn from the study
- Patients having received less than 50% of the study medication

Data of withdrawn patients will be included up until the moment of withdrawal. If measurements are recorded after withdrawal when not completed the appropriate duration of active treatment, these measurements will be considered as missing. For analysis of the primary endpoint, all data available will be used for analysis and imputation of missing values will be performed. More specifically, drop-outs will be considered as non-responders in all outcome measures (primary and secondary endpoints where linear mixed models will be used, and in the number of patients exceeding reference ranges). Only in the analyses of percentage changes of BMD and percentage of patients with a BMD loss higher than the least significant change, drop-outs will be considered as true drop-outs.

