11.1 Efficacy analysis

Complete and specific details of the final statistical analysis will be described and fully documented in the Statistical Analysis Plan (SAP). The SAP will be finalized prior to the database lock. The analysis will be performed using the statistical software package IBM SPSS. Demographic and baseline characteristics will be summarized. The number of observations, mean, standard deviation, median, minimum and maximum will be summarized for continuous variables. Discrete variables will be summarized by counts and percentages.

Primary analysis will be a per protocol approach, including all patients who completed the final visit (week 48). Missing data related to exploratory endpoints will be handled by last observation carried forward (LOCF) procedure.

The primary efficacy variables will be the number of patients that maintain CTx-I within the premenopausal reference range at week 48. Secondary efficacy variables will be the changes from baseline to week 12, 24 and 48 for CTx-I and P1NP levels. Co-exploratory variables will be DXA changes from baseline to week 24 and 48. Hand OA-related exploratory efficacy variables will be changes in NRS pain from baseline to week 12, 24 and 48, and changes in number of new erosive joints on X-rays and changes in GUSS values from baseline to W24 and 48.

All analyses be summarized by treatment group where treatment group equals 'exposed to Alendronate for 48 weeks Vs Alendronate for 24 weeks'.

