#### 2.3 Study design

This is a monocentric randomized study to investigate the effect of effervescent alendronate on bone turnover markers after denosumab discontinuation. At the earliest three months but no later than

four months after the last denosumab injection, 40 subjects will be randomized to effervescent alendronate administered for either 24 (n=20) or 48 weeks (n=20). The randomization was performed by a randomization manager. The total treatment duration per subject is 48 weeks.

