#### 4.2 Secondary endpoints

Secondary end points are changes in bone mineral density (BMD) at the femoral neck and spine at week 48, the number of patients from both groups maintaining CTX-I and PINP levels within reference range values at week 12, 24 and 48. Reference ranges used will be adjusted according to menopausal status and sex. Percentage changes in BMD and the percentage of patients with a BMD loss higher than the least significant change (LSC), which represents the smallest difference between successive measurements of BMD that can be considered a real change, will be calculated.

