### 5.2 Primary outcome analysis

The primary outcome analysis will be performed in an intention to treat approach, where drop-outs were considered as non-responders. Changes in bone turnover marker levels will be analysed with a linear mixed model. Data from all available time points will be used. Normal distribution will be checked and data transformations will be performed if necessary if assumptions of normality aren't reached. P-values and estimated marginal means will be calculated at different time points.

All analyses will be performed with a two-sided p-value. A p-value below 0.05 (p<0.05) will be considered statistically significant.

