#### 5.3 Secondary outcome analysis

Bone density measures will be analysed in an intention to treat approach, using a linear mixed model. Data from all available time points will be used. Normal distribution will be checked and data transformations will be performed if necessary if assumptions of normality are not reached. P-values and estimated marginal means will be calculated at different time points.

In addition, percentage changes in BMD and the percentage of patients with a BMD loss higher than the least significant change (LSC), which represents the smallest difference between successive measurements of BMD that can be considered a real change, will calculated. Here no intention to treat approach will be used.

The number of patients exceeding reference ranges will be calculated with an intention to treat approach, where drop-outs will be considered as non-responders. A Fisher's exact test was used to assess differences in patient numbers exceeding reference ranges between both treatment groups.

All statistical tests were two-tailed and a p-value below 0.05 ( $\alpha$ ) was considered statistically significant.

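### SAP 3.2.3 and 5.2 impute drop-outs as non-responders in linear mixed models of continuous markers without giving a value; models on observed data would serve better than any fixed unfavourable value.

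*SAP*

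**What the plan says.** The SAP's primary endpoint (4.1) is the between-arm difference in CTX-I and PINP after 48 weeks, and 5.2 analyses marker levels with a linear mixed model. SAP 3.2.3 announces imputation of missing values for the primary endpoint and then specifies that "drop-outs will be considered as non-responders in all outcome measures (primary and secondary endpoints where linear mixed models will be used", adding the counts of patients outside the reference range. SAP 5.2 restates it: "The primary outcome analysis will be performed in an intention to treat approach, where drop-outs were considered as non-responders".

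Bone density comes under the same rule, because SAP 5.3 states "Bone density measures will be analysed in an intention to treat approach, using a linear mixed model". The only exemptions are percentage change in BMD and the "percentage of patients with a BMD loss higher than the least significant change, drop-outs will be considered as true drop-outs".

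Two other rules come near the gap. SAP 4.2 says "Reference ranges used will be adjusted according to menopausal status and sex"; the limits are in the footnote to protocol section 2 (CTX-I below 700, 730 or 695 ng/L for non-menopausal women, menopausal women and men). Protocol 11.1 says "Missing data related to exploratory endpoints will be handled by last observation carried forward (LOCF) procedure".

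**The concern.** Non-responder imputation is a rule for a binary outcome. It works for the reference-range counts compared by Fisher's exact test in SAP 5.3: a drop-out is counted as out of range. In a model of ng/L or g/cm² a number must be entered, and candidates include a reference limit, the worst observed value or an earlier value of the patient's own. The SAP names none of these.

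Two things are at stake. First, the primary p-value can depend on a choice that the plan leaves open. Second, even a sensible reading of the rule, one unfavourable value for every drop-out, gives the wrong answer to the SAP's own question. If the arms lose different numbers of patients, drop-out appears as a drug effect. If they lose equal numbers, a real difference shrinks. In both cases a cluster of identical extreme values appears at week 48 only.

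**Working it through.** **Is there a value anywhere?**
- *Leave missing and let the model handle it.* Excluded: SAP 3.2.3 says imputation is performed and contrasts non-responders with true drop-outs, a status kept for two BMD analyses.
- *Use the reference limit.* SAP 4.2 and the protocol footnote use the limits to classify patients, not as values to impute. Modelled BMD has no such limit.
- *Use the protocol's rule.* Last observation carried forward is confined to exploratory endpoints, and the protocol's primary analysis includes only patients who completed week 48.

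So no value is given. The plan states no power or drop-out figure to reproduce; what follows is illustration.

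**Inputs.** From the documents: 20 per arm, two-sided 0.05, visits at weeks 0, 12, 24 and 48, limit 700 ng/L. Assumed: CTX-I medians 120/200/240/280 ng/L, log-SD 0.45, within-patient correlation 0.5, random exit before week 48, random-intercept model with constant variance on log CTX-I. The low exit rates come from the 6.4% per year stopping weekly 70 mg for adverse events in men (protocol 4.8): 6.4 × 24/52 = 3.0% and 6.4 × 48/52 = 5.9%. That figure omits other reasons for exit and may be low. The 10% and 19% rates have no anchor in the documents.

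**Bias, equal arms, 700 ng/L entered.** Once the missing values are filled in, the week-48 model estimate is the difference in arm means. The expected log shift is therefore (difference in exit rate) × ln(700/280), with ln(700/280) = 0.916.
- 3.0% vs 5.9%: 0.029 × 0.916 = 0.027, ratio 1.03.
- 10% vs 19%: 0.09 × 0.916 = 0.082, ratio 1.09. Entering 695 or 730 instead gives 1.086 to 1.090.

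**Dilution, equal exit p, medians 400 vs 280.** The expected log ratio is (1 − p) × ln(280/400) = (1 − p) × (−0.357).
- p = 10%: −0.321, so the ratio moves from 0.70 to 0.73.

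**Week-48 variance, equal arms.** With a fraction p at 700, variance = (1 − p) × 0.2025 + p(1 − p) × 0.916².
- p = 5.9%: 0.1906 + 0.0466 = 0.237, which is 17% above 0.2025.
- A constant-variance model averages over four visits: (3 × 0.2025 + 0.237)/4 = 0.211. The standard error is too small by √(0.211/0.237) = 0.944. The effective critical value is 1.96 × 0.944 = 1.85, which gives a two-sided error of about 6.4%.

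**Simulation on the same assumptions (700 ng/L entered).**

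| Scenario | Result |
|---|---|
| Equal arms, no drop-out | type I error about 5.3% |
| Equal arms, 5.9% exit in both | type I error about 6.6–7.0% |
| Same exit, week-48 t-test | type I error 5.1% |
| 400 vs 280, no drop-out | power about 70% |
| 400 vs 280, 5% exit in both | power 65% (70% on observed data) |
| 400 vs 280, 10% exit in both | power about 60% (67% on observed data) |

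Part of the power loss comes from missing data as such. The loss due to imputation is the gap from the observed-data figure: about 5 points at 5% exit and 7 at 10%.

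**Second set of assumptions** (raw scale, week-48 means 400 vs 300 ng/L, drop-outs 1 vs 3). The imputed values shift the arm means by 1 × (700 − 400)/20 = 15 and 3 × (700 − 300)/20 = 60. The expected difference is therefore −100 + 60 − 15 = −55. Simulation of 200 data sets gave −54.7, with p<0.05 in 29%; with the values left missing it gave −99.7 and 75%.

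**The case against.** The strongest reply is that non-responder has a natural meaning here, an unfavourable value near or above the reference limit, and that within that family the choice matters little. This largely stands. With medians 400 vs 280 and 5% or 10% exit, the verdict on p<0.05 differs from that with 700 ng/L in under 1% of trials if 695 or 730 is entered, 4–5% with the worst observed value, and 5–6% with 1000 ng/L. It does not rescue the rule, because the bias and power loss shown above arise with 700 itself.

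The type I excess also depends on a constant-variance model, which SAP 5.2 does not specify.

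Four stronger readings are tempting but not supported:
- *The primary analysis cannot be run at all.* With no drop-outs nothing is imputed, and no drop-out rate is given.
- *The open choice can swing the result either way in a quarter to a third of trials.* That comparison sets 700 ng/L against the patient's own baseline. Baseline falls three to four months after the last denosumab injection, and on the assumed values it is the lowest point. Entering it would score a drop-out as a success, which fits non-responder poorly.
- *The value was chosen to suit the result.* Nothing in either document shows this.
- *The deletion rule is part of the same defect.* SAP 3.2.3 also says "If measurements are recorded after withdrawal when not completed the appropriate duration of active treatment, these measurements will be considered as missing". That rule can be carried out as written and is a separate, minor matter.

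A sponsor may also say that observed-data models change the estimand. That is fair, and the SAP should say so openly.

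**Conclusion.** The point holds, at SHOULD-FIX. The SAP imputes a responder category into continuous models, gives no value for CTX-I, PINP or BMD, and excludes the reading under which drop-outs are left missing. This is more than an omitted detail, since the most natural value to enter does harm.

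On the assumed values the harm is small at the only exit rates with any anchor in the documents (ratio about 1.03 when the arms are equal) and material at higher ones (1.09 at 10% vs 19%; about 7 points of power at 10% in both arms). It is nil with no drop-outs. These sizes rest on the assumed medians, SD, correlation and random exit. The absence of a stated value does not depend on any of them.

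**What to change.** In SAP 3.2.3, 5.2 and 5.3:
1. Remove non-responder imputation from every mixed-model outcome. Fit the models to all observed data, with patients in the arm as randomised.
2. Keep non-responder status only for the reference-range counts and Fisher's exact test.
3. Add one sensitivity analysis for CTX-I and PINP. Set each missing week-48 value to the less favourable (higher) of the model-predicted value and the patient's own upper reference limit, first in the 24-week arm only, then in the 48-week arm only, then in both. Taking the higher of the two avoids pulling a patient predicted above the limit back towards it.

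For scale, take 10% missing per arm, predictions at medians 400 vs 280 and a limit of 700 ng/L. The ratio of 0.70 would become:
- 48-week arm only: exp(−0.357 + 0.1 × 0.916) = 0.77.
- 24-week arm only: exp(−0.357 − 0.1 × ln(700/400)) = exp(−0.357 − 0.056) = 0.66.
- Both arms: 0.73.

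The cost is SAP wording and one extra analysis; no new data are needed. The downside is that the main model relies on missing at random, which the sensitivity analysis examines.

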## 4. Outcome measures

#### 4.1 Primary endpoints

The primary end point of this study is to investigate if effervescent alendronate is able to maintain bone turnover markers after discontinuation of denosumab in a non-osteoporotic population. The outcome measures being used for this are the bone turnover markers CTX-I (C-terminal telopeptide of type I collagen) a marker that reflects the breakdown of bone and PINP (N-terminal propeptide of type I collagen) a marker that reflects the formation of new bone. The primary end point will be the difference in these bone turnover markers after 48 weeks between both treatment arms.

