Main Endpoints	 The primary endpoint of this objective is to assess the number of patients that maintain C-terminal telopeptide of type I collagen (CTx-I) levels within the premenopausal reference range at 48 weeks. Secondary endpoints are the assessment of the number of patients that maintain CTx-I levels within the premenopausal reference range at week 12 and 24 as well as the changes in CTx-I and N-terminal propeptide of type I procollagen (P1NP) levels from baseline until 12, 24 and 48 weeks after randomization to effervescent alendronate. Co-exploratory objectives are changes in T-score at lumbar spine and hip from baseline to week 24 and week 48, and the radiographic changes at the finger joints in terms of new erosive joints and GUSS change between W24 and W48 and baseline. 				
Hypothesis	The main hypothesis is that effervescent alendronate will be able to maintain bone turnover markers within the pre-menopausal reference range, thereby reducing the likelihood of bone turnover associated changes.				
Study Sites	1 site – the UZ Ghent site				
Subjects	40 subjects for the alendronate follow-up study				
Enrolment	72 weeks				
Main Eligibility Criteria	Subject must have completed our three year study 'RANKL-blockade for the treatment of erosive osteoarthritis (OA) of interphalangeal finger joints' (EudraCT number: 2015-003223-53; Protocolnumber: AGO/2015/008)				
Study treatment Duration	48 weeks				

Table of Contents

- Protocol Title and Investigators
- Protocol signature page
- Protocol synopsis

1. Background and Rationale

- 1.1 Disease background
- 1.2 Denosumab
- 1.3 Effervescent alendronate
- 1.4 Rationale for study design
- 1.5 Hypotheses

2. Study Objectives and Endpoints

3. Experimental Plan

- 3.1 Study design and schematic
- 3.2 Number of sites
- 3.3 Number of subjects
- 3.4 Estimated study duration
- 3.5 Subject Eligibility
 - 3.5.1 Inclusion criteria
 - 3.5.2 Exclusion criteria
- 3.6 Criteria for withdrawal

4. Medication

- 4.1 Composition and dosing
- 4.2 Producer
- 4.3 Distributor
- 4.4 Packaging
- 4.5 Administration way
- 4.6 Labelling:
- 4.7 Storage conditions:
- 4.8 Known side effects of the medication
- 4.9 Drug accountability

5. Procedures

- 5.1 Study procedures
- 5.2 Study table
- 5.3 Sample processing

6. Randomisation

7. Reporting requirements for investigational product complaints

- 8. Concomitant therapy
- 9. End of study
- 10. Adverse Events/Adverse Event reporting
 - 10.1. Definitions

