1.5 Hypotheses

It is hypothesized that effervescent alendronate will be able to maintain bone turnover markers within the pre-menopausal reference range thereby reducing the likelihood of bone turnover associated changes, after discontinuation of Prolia treatment in a non-osteoporotic population.

2. Study Objectives and Endpoints

The objectives of the effervescent alendronate treatment after denosumab discontinuation are to investigate if weekly intake of effervescent alendronate can prevent increases in bone turnover above the premenopausal reference range^{*} at week 48 and if there is difference between using alendronate for 24 or 48 weeks, started at the earliest three months but no later than four months after the last injection of denosumab.

Other objectives of the study are:

- to assess the changes in bone turnover after 12 and 24 weeks,
- to explore the impact on dual-energy X-ray absorptiometry (DEXA) parameters after 24 and 48 weeks of treatment
- to assess radiographic changes and investigate if new erosive joints develop at week 24 and 48

The primary endpoint of this objective is the number of patients that maintain C-terminal telopeptide of type I collagen (CTx-I) within the premenopausal reference range at 48 weeks.

Secondary endpoints are the number of patients that maintain CTx-I within the premenopausal reference range at week 12 and 24 as well as the changes in CTx-I and N-terminal propeptide of type I procollagen (P1NP) from baseline until 12, 24 and 48 weeks after randomization to effervescent alendronate.

Co-exploratory objectives are changes in T-score at lumbar spine and hip from baseline to week 24 and week 48, and related to the underlying erosive hand OA disease, the radiographic changes at the finger joints in terms of new (radiographic) erosive joints (n) and GUSS change (Δ) between W24 and W48 and baseline.

Safety-objective

This study will assess the safety of the weekly administration of effervescent alendronate 70mg in the population of patients with erosive OA. Safety evaluations will be made by recording the incidence of AE/SAE

^{*} Reference range: CTX-I (IVD kit) Non menopausal women < 700ng/l. Menopausal women < 730ng/l. Adult male >20 to 120 years: < 695ng/L; P1NP (IVD kit): Male > 45 years: 12.8-71.9 µg/L Non menopausal women: 13.7-71.1 µg/L Menopausal women: < $82.6 \mu g/L$

3. Experimental Plan

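### Protocol and SAP fix different primary endpoints and analysis sets, and the SAP does not say how its two primary markers combine

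*SAP*

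**What the plan says.** **Protocol.** Section 2 gives the primary endpoint as "the number of patients that maintain C-terminal telopeptide of type I collagen (CTx-I) within the premenopausal reference range at 48 weeks". Section 11.1 repeats it: "The primary efficacy variables will be the number of patients that maintain CTx-I within the premenopausal reference range at week 48". The same section sets the population: "Primary analysis will be a per protocol approach, including all patients who completed the final visit (week 48"). Marker changes rank second in section 11.1 ("Secondary efficacy variables will be the changes from baseline to week 12, 24 and 48 for CTx-I and P1NP levels"), and the synopsis lists them among the secondary endpoints: "as well as the changes in CTx-I and N-terminal propeptide of type I procollagen (P1NP) levels from baseline until 12, 24 and 48 weeks". Results are to be shown by arm ("All analyses be summarized by treatment group where treatment group equals" 48 versus 24 weeks of alendronate). No test or threshold is named for the count.

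**SAP.** Section 4.1 opens with the aim of finding out whether alendronate can maintain the markers, introduces CTX-I and PINP, and ends: "The primary end point will be the difference in these bone turnover markers after 48 weeks between both treatment arms". Section 5.2 analyses this with a linear mixed model under intention to treat, counts drop-outs as failures, and sets a two-sided 0.05 threshold. Section 3.2.2 limits the full analysis set to randomised patients with at least one dose. Section 4.2 lists the in-range count as secondary and extends it to PINP. Section 5.3 compares the out-of-range counts between arms with Fisher's exact test, again with drop-outs as failures.

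**The concern.** The two documents give one 40-patient trial two primary results, on two analysis sets. Three things are at stake.

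- **Pre-specification.** A reader of the report cannot tell which result was planned as primary unless the change is declared and dated.
- **The question answered.** Both documents hypothesise that markers stay within the reference range (protocol section 1.5, SAP section 2.2). A contrast between 24 and 48 weeks of treatment addresses the duration question, which is also part of the objective. It does not test the hypothesis.
- **The decision rule.** With two primary markers and no rule for combining them, a result in which only one is significant has no agreed reading.

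**Working it through.** Neither document gives a figure to reproduce: protocol section 11.3 states that no formal sample size calculation was made. The check is therefore a comparison of the texts, followed by illustrations on assumed inputs.

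**1. Texts side by side**

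| Item | Protocol (synopsis, 2, 11.1) | SAP (3.2.2, 4.1, 4.2, 5.2, 5.3) |
|---|---|---|
| Primary variable | CTx-I in range at week 48 (yes/no) | Between-arm difference in CTX-I and PINP at week 48 |
| Markers | One | Two |
| Analysis set | Week-48 completers | Randomised with at least one dose, called intention to treat |
| Drop-outs | Excluded | Counted as failures |
| Other endpoint | Marker changes secondary | In-range count secondary |

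The completer analysis of the count does not appear anywhere in the SAP text available.

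**2. Analysis set and the count** (two-sided Fisher test, 20 per arm, invented counts)

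- Two drop-outs per arm: 18/18 vs 13/18 in completers, p=0.046; 18/20 vs 13/20 with drop-outs as failures, p=0.127.
- Drop-outs in one arm only (0 vs 5): 19/20 vs 12/15, p=0.29; 19/20 vs 12/20, p=0.020.
- A case that agrees: 18/18 vs 14/18, p=0.104; 18/20 vs 14/20, p=0.235.

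The choice of set can move the result in either direction. The first two cases were chosen to show this.

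**3. Two markers, each at 0.05**

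If either suffices, the error with independent markers is 1 − 0.95² = 9.75%. For a bivariate normal with correlation 0.8 it is 7.8%. If both are required there is no inflation.

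**4. What a between-arm difference can show**

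Take CTX-I as log-normal with an assumed log-SD of 0.5 and the 700 ng/L limit from the protocol footnote. The expected share in range is Φ(ln(700/median)/0.5).

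- Median 300: Φ(1.69) = 95%.
- Median 500: Φ(0.67) = 75%.
- Median 800: Φ(−0.27) = 39%.

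Two arms both at 300 and two arms both at 800 have the same true difference, zero, yet the in-range share is 95% in one case and 39% in the other.

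**5. Which endpoint is primary** (20,000 simulated trials per scenario, 20 per arm, same assumptions, no drop-outs, t-test on log values standing in for the week-48 mixed-model contrast, Fisher test for the count)

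| Medians (ng/L) | Continuous test significant | Count significant | Verdicts differ |
|---|---|---|---|
| 300 vs 500 | 88% | 32% | 57% |
| 400 vs 500 | 28% | 9% | 23% |
| 300 vs 800 | 100% | 98% | 2% |

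The count alone was significant in about 0.5%, 1.9% and 0% of trials respectively. The gap is therefore mainly the power lost by dichotomising.

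**The case against.** The protocol leaves full analysis details to the SAP, an intention-to-treat set and a continuous endpoint are defensible at this size, and the SAP still reports the count by arm and marginal means over time. Much of this stands, and the continuous endpoint may be kept. But protocol section 11.1 itself fixes the primary variable and population, and replacing both is more than detail. The completer analysis of the count has also gone.

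Four stronger readings are tempting, and the documents do not support them.

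- *The change was concealed or made after seeing data.* The SAP's contents list a section 1.2 on SAP details that was not available, so a declaration there cannot be excluded. Protocol section 5.3 sends stored tubes to an external laboratory at study end, but section 5.1 also lists bone turnover markers among the visit tests, so it is not clear when results existed. The SAP's reference list carries a 2024 citation, later than its own timeline. This is a reason to ask for a date, but it does not show when the endpoint was set.
- *The SAP has no success criterion.* It sets two-sided p<0.05. What is missing is the rule for combining two markers. The protocol's own primary has no named test or threshold either.
- *The two endpoints lead to opposite conclusions.* Section 5 of the working shows a power difference, and its size depends on the assumed medians.
- *The reference range was changed.* The protocol says premenopausal, but its footnote already gives limits by group ("Menopausal women < 730ng/l. Adult male >20 to 120 years: < 695ng/L", with 700 ng/L for non-menopausal women), which fits the SAP's adjustment for sex and menopausal status. This is at most a minor wording point.

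**Conclusion.** The point holds. The protocol and the SAP name different primary endpoints on different analysis sets, and the SAP text available neither declares the change nor says whether one marker or both must be significant. This should be settled before any result is labelled primary.

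The textual conflict rests on no assumption. Its numerical effect does, because the documents give no drop-out rate, marker SD or expected proportions. Depending on the pattern of drop-out, the analysis set can create or remove significance for the count. An either-marker rule would carry 7.8% to 9.75% error. Endpoint choice changes the verdict in anything from 2% to 57% of trials across the scenarios tried. The conclusion about non-declaration is conditional on what SAP section 1 contains.

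**What to change.** 1. Name a single primary in SAP sections 4.1 and 5.2. Either restore the protocol's week-48 CTx-I in-range count, or keep the continuous endpoint as a declared change. In the second case, make CTX-I at week 48 alone primary or state that both markers must be significant.
2. Unless SAP section 1 already does so, state in the SAP and the report that the primary endpoint and analysis set differ from protocol version 1.0, when each was changed, and whether any marker results had been seen by then.
3. In either case, report the protocol's endpoint, labelled as the protocol-specified primary. Give each arm's in-range proportion with an exact 95% CI and the between-arm difference with a CI, both in week-48 completers and in the full analysis set with drop-outs counted as not in range.

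**Cost.** Wording and a small extra analysis, with no new data. If the count is primary, power is lower: Fisher's test needs, for example, 20/20 vs 15/20 (p=0.047), while 20/20 vs 16/20 gives p=0.106. If both markers are required and each has 80% power, joint power is 0.8 × 0.8 = 64% when independent and 73% at correlation 0.8. Naming CTX-I alone avoids that loss.

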## 2.2 Hypothesis and objectives

It is hypothesized that effervescent alendronate will be able to maintain bone turnover markers within the reference range thereby reducing the likelihood of bone turnover associated changes, after discontinuation of denosumab treatment in a non-osteoporotic population.

The **primary objective** of this study is to assess the effect of effervescent alendronate after denosumab discontinuation on the change in bone turnover markers after 48 weeks in a non-osteoporotic population and to assess if there is a difference between using oral alendronate after 24 or 48 weeks.

The **secondary objective** is to evaluate the effect of effervescent alendronate after denosumab discontinuation on bone mineral density in this non-osteoporotic population and assess difference in oral alendronate therapy for 24 versus 48 weeks.

**Exploratory objectives** are to study the effect of oral alendronate therapy after denosumab discontinuation on erosive destructive progression at the subchondral bone in erosive hand OA patients and to assess the effect of oral alendronate on their hand pain scores.

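### The hypothesis asks whether alendronate keeps markers in range, but the SAP's primary end point is a difference between two alendronate arms, which answers only the 24 versus 48 week question

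*SAP*

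**What the plan says.** SAP 2.2 states the hypothesis without a comparator: "It is hypothesized that effervescent alendronate will be able to maintain bone turnover markers within the reference range". Protocol 1.5 says the same, with the premenopausal range named. The SAP's primary objective then has two parts: the effect on markers after 48 weeks, and "to assess if there is a difference between using oral alendronate after 24 or 48 weeks".

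SAP 4.1 begins with the absolute question, to "investigate if effervescent alendronate is able to maintain bone turnover markers after discontinuation of denosumab". It ends with a relative measure: "The primary end point will be the difference in these bone turnover markers after 48 weeks between both treatment arms". The markers are CTX-I and P1NP.

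SAP 5.2 gives the method: "Changes in bone turnover marker levels will be analysed with a linear mixed model". The output is: "P-values and estimated marginal means will be calculated at different time points". The decision rule is: "A p-value below 0.05 (p<0.05) will be considered statistically significant". The contrast to be tested is not named, and neither an interval nor a comparison with the reference limit is specified.

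Protocol 2 and 11.1 define a different primary endpoint: the number of patients whose CTX-I is within the premenopausal range at week 48. SAP 4.2 makes in-range counts (CTX-I and P1NP; weeks 12, 24 and 48) secondary. SAP 5.3 tests the number of patients exceeding the range with Fisher's exact test between the two groups.

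SAP 2.3 describes two arms of 20, both on alendronate, for 24 or 48 weeks. There is no untreated arm. Protocol 11.3 says that no formal sample size calculation was done.

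**The concern.** A contrast between two active arms removes whatever the arms have in common. If both hold their markers in range, the difference is near zero. If both rebound after denosumab, it is also near zero. A significant difference does not settle the matter either, because two arms can differ while both mean levels lie below the limit or both lie above it. The primary end point therefore answers the second half of the SAP's objective and leaves the hypothesis without a matching primary estimate.

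Two misreadings are at stake. A non-significant primary result could be presented as markers maintained, or as 24 weeks being as good as 48. The SAP contains nothing that guards against either.

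**Working it through.** The plan states no power, margin or success threshold, so there is no figure of its own to reproduce. Inputs from the documents are 20 per arm (SAP 2.3), two-sided 0.05 (SAP 5.2), Fisher's exact test (SAP 5.3), and CTX-I limits of 700, 730 and 695 ng/l for non-menopausal women, menopausal women and men (Protocol 2, footnote). All counts, means and SDs below are assumptions.

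**1. Which text asks which question.**

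| Source | Absolute (in range?) | Relative (24 v 48 weeks?) |
|---|---|---|
| Hypothesis, Protocol 1.5 and SAP 2.2 | yes | no |
| Protocol primary endpoint | yes | no |
| SAP 4.1, opening purpose | yes | no |
| SAP 4.1, primary end point as defined | no | yes |
| SAP 5.3, test of the counts | no | yes |

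**2. In-range counts (the SAP's secondary test).** The exact (Clopper-Pearson) 95% limits for x of n are the 2.5% point of Beta(x, n−x+1) and the 97.5% point of Beta(x+1, n−x).
- 18/20 v 18/20: Fisher p=1.0; each arm 68% to 99%.
- 8/20 v 8/20: Fisher p=1.0; each arm 19% to 64%.
- 20/20: lower limit 83%.

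The first two cases give the same p-value and opposite answers to the hypothesis. Over repeated trials, P(p<0.05) is 1.2% when both true rates are 90% and the same 1.2% when both are 10%.

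**3. Marker levels (a stand-in for the primary contrast).** This uses a two-sample t-test at week 48 with an assumed SD of 200 ng/l, simulated 20,000 times.
- Both means 350 (held): rejects about 5%.
- Both means 1000 (rebounded): rejects about 5%.
- 350 v 600, both means below 700: rejects 97%.
- 750 v 1000, both means above 700: rejects 97%.

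The last two agree because the standardised difference is the same: 250/200 = 1.25 SD. A one-sample comparison of the arm mean with 700 ng/l separates the first two cases. It declares the mean below the limit in 100% of runs at 350 and 0% at 1000.

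**4. Precision for the duration question.** This is an unadjusted t-test with 20 per arm and no drop-out.
- 95% half-width = t(0.975, 38 df) × √(2/20) × SD = 2.024 × 0.316 × SD = 0.64 SD.
- Power at 0.5 SD (noncentral t, noncentrality 0.5 × √10 = 1.58): 34%.
- Difference needed for 80% power: 0.91 SD.

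If baseline is adjusted for, the SD shrinks by √(1−r²). An assumed correlation r of 0.5 to 0.7 gives a half-width of 0.55 to 0.46 SD, and power at 0.5 SD of 43% to 58%. Drop-out works the other way. With an assumed 16 per arm and no adjustment, the half-width is 2.042 × √(2/16) = 0.72 SD.

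**The case against.** The strongest reply is that absolute information is already planned. SAP 5.2 calls for marginal means by time point. Given per arm, these would separate two arms that hold from two that rebound. SAP 4.2 keeps the in-range counts, and SAP 5 summarises categorical data as counts and percentages, so a reader who knows n can work out an exact interval. Because SAP 5.2 names no contrast, its p-values might also include within-arm changes.

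Most of this stands, and it limits the point. A reader might infer that the trial will produce nothing bearing on its hypothesis. The documents do not support that: the data will exist and can be read descriptively. What remains is the counts' secondary rank, the missing intervals, and the absence of any named test or criterion aimed at the hypothesis. Marginal means do not fill that gap. A mean below a limit does not show that individual patients stayed below it, and the limits differ by sex and menopausal status. A within-arm p-value would test zero change from a baseline taken three to four months after the last denosumab injection, which is not the same as staying in range.

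Three further cautions hold. A significant difference need not appear when one arm does worse: 18/20 v 12/20 gives Fisher p=0.065. The Fisher examples concern the secondary test, and the t-test figures only approximate the mixed model. Finally, Protocol 11.3 openly says that the sample was capped by the parent study, so limited precision is no concealed fault.

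**Conclusion.** The point holds as a mismatch between question and primary estimate. The hypothesis and the protocol's primary endpoint are absolute, while the SAP's primary end point is relative. No named test, primary or secondary, addresses whether markers stay in range. The logic needs no assumption beyond the design: both arms are treated and none is untreated. The size of the ambiguity is shown by identical p-values of 1.0 for per-arm intervals of 68-99% and 19-64%. For duration, the half-width is about 0.64 SD and power is 34% at 0.5 SD. Those two figures rest on an unadjusted comparison of 20 v 20 with no drop-out.

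A reader might go further and infer that the sponsor intends to claim equivalence of the two durations. Neither document makes an equivalence or non-inferiority claim. The point is only that the SAP does not rule that reading out. The change is worth making because the planned data can answer the trial's own question and the primary analysis as written does not.

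**What to change.** Amend SAP 4.1, 5.2 and 5.3 so that each question has its own estimate.

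1. **Maintenance.** Restore the protocol's primary endpoint: the proportion with CTX-I in range at week 48, per arm, with an exact 95% interval. Report P1NP the same way as supportive. Say what each proportion measures. In the 48-week arm it is maintenance on treatment. In the 24-week arm it is persistence 24 weeks after stopping (48 − 24). State that without an untreated arm the result is descriptive and does not prove that alendronate caused it. The documents give no success benchmark; if one is wanted, the sponsor should set and justify it in advance.
2. **Duration.** Name the week-48 between-arm difference from the mixed model as the contrast, and report it with its 95% interval.
3. **Interpretation.** State that p>0.05 will not be reported as maintenance or as equivalence of the two durations.

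The cost is SAP wording and a few output lines, with no new data. The maintenance claim will look slightly less favourable because its interval is shown: even 20/20 leaves true rates down to 83% possible.
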